## 2. INTRODUCTION

### 2.1 Background, Significance, and Rationale

Chronic kidney disease (CKD) is associated with hypertension and diabetes and affects 26 million US adults. African Americans (AA's) have higher risk of end stage renal disease (ESRD) necessitating maintenance dialysis or transplant than Whites. This disparity widens as kidney function declines. Additionally, AAs have the highest prevalence of hypertension (41% AA, 28% White) and the lowest rate of blood pressure (BP) control (43% AA versus 53% White). While improved BP control decreases CKD progression and reduces morbidity and mortality, BP control (defined as < 140/90 mm Hg) is only achieved in 50% of participants.

One in 7 AAs carry the Apolipoprotein L1 (*APOL1*) gene risk allele, but it is nearly absent in other populations. High-risk variants in the *APOL1* explain approximately 70% of the excess prevalence of CKD in AAs, conferring a 5 times higher risk for hypertensive CKD and a 10 times higher risk for ESRD. This risk is conferred by two variants (G1 and/or G2) in the last exon of *APOL1* with the high-risk genotype being G1/G1; G2/G2 or G1/G2. *APOL1* does not significantly increase CKD risk in hypertensive people with diabetes and normal renal function, but in hypertensive people with prevalent CKD, *APOL1* exacerbates worsening of kidney function and progression to ESRD regardless of diabetes diagnosis. Among adults with CKD, specific medications (angiotensin-converting enzyme (ACE) inhibitors or angiotensin receptor blockers (ARBs)) are recommended for participants of all ancestries, but 50% of participants do not receive these medications. Compounding this issue is the fact that providers do not include CKD on the problem list of 40% of participants with lab evidence of CKD, leading to widespread participant unawareness of CKD. Urine protein tests, essential for early diagnosis and prognosis of CKD, are missing in up to 30% of participants with CKD.

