## 9. STATISTICAL ANALYSIS PLAN AND SAMPLE SIZE

### 9.1 Sample Size Determination

#### Main Study

In GUARDD, there was a 13% prevalence of *APOL1* positive individuals among hypertension participants and a standard deviation of 18.1 mm Hg for SBP. A separate unpublished pilot study from Indiana University showed a 20% prevalence of *APOL1* positive individuals among participants with CKD and an estimated CKD prevalence of 50%. Finally, another study showed a 26% prevalence of *APOL1* positive AAs with CKD. As such, the initial sample size determination assumed a 17% prevalence of *APOL1* positive individuals. However, observation of the prevalence of the *APOL1* positive study participants during the course of the study led investigators and the DSMB to believe that this assumption was too high and the actual prevalence in the study population was between 14 and 15 percent. Assuming a conservative 14% prevalence of *APOL1* positive individuals based on these studies, a sample size of approximately 6700 for the randomized population would result in approximately 938 *APOL1* positive individuals with at least 469 in each arm for the main study population examined here. Using a two tailed t-test and assuming an overall 5% level of significance, 10% lost-to-follow up, two interim analyses, and a standard deviation of 18.1 mm of Hg, a sample size of 6700 for the randomized population and approximately 938 for the *APOL1* positive individuals will detect a 3.5 mm Hg difference in the change in SBP from baseline to 3 months between Intervention - *APOL1* positive and Control - *APOL1* positive groups with at least 80% power. This sample size determination assumes 10% of the 938 *APOL1* positive individuals could drop out of the study before 3 months and therefore have incomplete data on SBP change from baseline to 3 months. *APOL1* positive individuals with incomplete data on SBP change from baseline to 3 months cannot be included in the primary endpoint analysis. Therefore, the final analysis on the primary endpoint needs at least 844 *APOL1* positive individuals who have complete data for SBP change from baseline to 3 months to detect a 3.5 mm Hg difference between two treatment groups. Enrollment will continue until the 844 target can be ensured. Since *APOL1* and SBP data could be missing for various reasons, approximately 50 additional participants will be randomized to help us to reach this 844 target. This makes the total randomization target to be approximately 6750. Enrollment may end prior to the 6750 target if the study team is certain that the necessary 844 *APOL1* positive individuals with complete SBP change data can be achieved.

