## **9.5 Analysis of the Secondary Endpoints**

The effect of knowledge of a positive *APOL1* status on secondary endpoints [i.e., change in urine microalbuminuria/proteinuria orders from baseline to 6 months (Y/N), documented order of microalbuminuria/proteinuria tests by 6 months (Y/N), change in documented diagnosis for stage 3 CKD and above (Y/N) from baseline to 6 months, documented diagnosis of CKD stage 3 and above by 6 months (Y/N), change in documented diagnosis for any stage CKD from baseline to 6 months (Y/N), and documented diagnosis of all stages of CKD by 6 months (Y/N) ] will be compared between Intervention - *APOL1* positives and Control - *APOL1* positives with the proportion difference test.

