### 10.2 Data Element Definitions

Baseline SBP will be defined as the mean of the 2nd and 3rd measurements taken according to the GUARDD-US Blood Pressure Protocol provided in the MOP. Similarly, follow-up SBP will be the average of the 2nd and 3rd SBP measures at the follow-up visit, or alternatively the SBP from the EHR entered into the study database by the site in accordance with the study manual of procedures (MOP).

Secondary Endpoints will be defined as follows:

1. Change in urine microalbuminuria/proteinuria orders from baseline to 6 months (Y/N)
  - a. Order of urine microalbuminuria/proteinuria test at baseline is a binary variable (Y/N) where 'Y' is defined as the presence of urine proteinuria or urine microalbuminuria diagnostic code (i.e. 82043/84156 (Current Procedural Terminology (CPT) codes) OR the presence of urine microalbuminuria/proteinuria lab test order and/or result in the participant's EHR record at any point in the 12 months prior to baseline.
  - b. Order of urine microalbuminuria/proteinuria test at 6 months is a binary variable (Y/N) where 'Y' is defined as the presence of urine proteinuria or urine microalbuminuria diagnostic code 82043/84156 (CPT codes) OR the presence of urine microalbuminuria/proteinuria lab test order and/or result in the participant's EHR record at any point from baseline to 6 months.

- c. Change in urine microalbuminuria/proteinuria orders is a binary variable (Y/N) where 'Y' is defined as no order of urine microalbuminuria/proteinuria test at baseline and having an order of urine microalbuminuria/proteinuria test at 6 months [No for 1a, Yes for 1b = NY].

2. Documented order of microalbuminuria/proteinuria tests by 6 months is a binary variable (Y/N) where 'Y' is defined as the change in urine microalbuminuria/proteinuria orders (as described in 1c) OR (order of urine microalbuminuria/proteinuria test at baseline) [NY, YN or YY]

3. Change in documented diagnosis for stage 3 CKD and above from baseline to 6 months (Y/N)

- a. Documented diagnosis at baseline is a binary variable (Y/N) where 'Y' is defined as [the presence of a CKD ICD10 diagnosis codes of N18.3 – N18.5 in the 24 months prior to baseline].
- b. Documented diagnosis at 6 months is a binary variable (Y/N) where 'Y' is defined as [the presence of a CKD ICD10 diagnosis codes of N18.3 – N18.6 in the 6 months after baseline].

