- c. Change in documented diagnosis for stage 3 CKD and above is a binary variable (Y/N) where 'Y' is defined as no documented diagnosis at baseline and documented diagnosis at 6 months [No for 3a, Yes for 3b = NY].

4. Documented diagnosis of stage 3 and above CKD by 6 months is a binary variable (Y/N) where 'Y' is defined as (change in documented diagnosis for stage 3 CKD (as described in 3c)) OR (documented diagnosis at baseline (as described in 3a)) [NY, YN or YY].

5. Change in documented diagnosis for any stage CKD from baseline to 6 months (Y/N)

- a. Documented diagnosis at baseline is a binary variable (Y/N) where 'Y' is defined as [the presence of a CKD ICD10 diagnosis code (i.e., N18.x; E08.22; E09.22; E10.22; E11.22; E13.22) in the 24 months prior to baseline].
- b. Documented diagnosis at 6 months is a binary variable (Y/N) where 'Y' is defined as [the presence of a CKD ICD10 diagnosis code (i.e., E18.x; E08.22; E09.22; E10.22; E11.22; E13.22) in the 6 months after baseline].
- c. Change in documented diagnosis for any stage CKD is a binary variable defined as no documented diagnosis at baseline and documented diagnosis at 6 months [No for 5a, Yes for 5b = NY].

6. Documented diagnosis of any stage CKD by 6 months is a binary variable (Y/N) where 'Y' is defined as (the change in documented diagnosis of any stage CKD (as described in 5c)) OR (documented diagnosis at baseline (as described in 5a)) [NY, YN or YY].

For CEA analyses, the following definitions for variables obtained from the EHR will be used:

1. 6-month CKD stage will be defined with the follow categories using the most recent GFR measurement obtained between baseline and 6 months:
  - a. Stage 1 with normal or high GFR (GFR > 90 mL/min)
  - b. Stage 2 Mild CKD (GFR = 60-89 mL/min)
  - c. Stage 3A Moderate CKD (GFR = 45-59 mL/min)
  - d. Stage 3B Moderate CKD (GFR = 30-44 mL/min)
  - e. Stage 4 Severe CKD (GFR = 15-29 mL/min)
  - f. Stage 5 End Stage CKD (GFR <15 mL/min)
2. 6-month blood cholesterol: The last observed blood cholesterol level observed prior to baseline. Missing values will be imputed.

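### The CKD-diagnosis change endpoints (3 and 5) score a new code in all APOL1 positives whatever their CKD status at entry, so the planned estimate cannot show what a difference means

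*Combined protocol and SAP*

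**What the plan says.** Section 2.1 describes the problem as under-documentation: "providers do not include CKD on the problem list of 40% of participants with lab evidence of CKD". Secondary aim 1 (Section 2.2) is the probability of a documented CKD diagnosis.

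Section 10.2 defines the two change endpoints by ICD-10 codes alone.

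- Endpoint 3 (stage 3 and above): success is "no documented diagnosis at baseline and documented diagnosis at 6 months [No for 3a, Yes for 3b = NY". The follow-up element is "the presence of a CKD ICD10 diagnosis codes of N18.3 – N18.6 in the 6 months after baseline"; the baseline element counts N18.3–N18.5 in the prior 24 months.
- Endpoint 5 (any stage): the change is a "binary variable defined as no documented diagnosis at baseline and documented diagnosis at 6 months". The baseline list reads "i.e., N18.x; E08.22; E09.22; E10.22; E11.22; E13.22) in the 24 months prior to baseline" and the follow-up list reads "i.e., E18.x; E08.22; E09.22; E10.22; E11.22; E13.22) in the 6 months after baseline". The first entry differs (N18.x against E18.x).

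Neither endpoint carries an eGFR or albuminuria condition at either time. Section 9.3 takes everyone randomized who tests APOL1 positive, and Section 9.5 compares the arms "with the proportion difference test", without stratification. Section 5.1 admits two kinds of participant: those with neither diabetes nor CKD, and those with CKD by code, albuminuria or eGFR. The only planned analysis by CKD status is the CKD subset in Section 9.6, which concerns SBP and is run only if the primary outcome differs.

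**The concern.** A participant with a qualifying code in the 24 months before baseline is already a yes and cannot convert. The pool that can convert therefore holds two groups: (i) people with CKD at entry and no qualifying recent code, and (ii) people enrolled as not having CKD. A new code in group (i) is the recognition that Section 2.1 says is lacking. A new code in group (ii) may be CKD newly found by testing, or a code with no laboratory support.

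Assignment is not blinded (Section 4.3). The laboratory report for a high-risk genotype states increased CKD risk (Table 1), and alerts to providers, where available, repeat the risk and prompt urine testing (Sections 7.1 and 7.8). Controls' results come only after the 6-month visit. All three routes to a new code can thus respond to the intervention, and all three score alike. These endpoints carry secondary aim 1, so what a difference means is as important as its size.

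**Working it through.** **Denominator (the plan's own figures).** 6700 × 0.14 = 938 APOL1 positives, 469 per arm; 938 × 0.90 = 844 with complete SBP data. The two-means formula with a 3.5 mm Hg difference, SD 18.1, two-sided alpha 0.0492 and 80% power gives 422 per arm, or 844. The figures reproduce, but they size the primary endpoint. No rate or power is stated for endpoints 3 and 5.

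**Inputs for the convertible pool, endpoint 5.**

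- k, the share of randomized participants with CKD: Section 9.1 cites a pilot with "an estimated CKD prevalence of 50" per cent.
- pC, APOL1-positive prevalence in CKD: 20% in that pilot (26% in another study), Section 9.1.
- APOL1-positive prevalence without CKD: 13%, from the GUARDD pilot, which excluded CKD (Sections 2.1 and 9.1).
- u, the share of CKD participants with no qualifying baseline code: 40%, borrowed from the problem-list figure in Section 2.1. This is an assumption, because a problem-list entry is not an ICD-10 code.
- Item 5b is read as N18.x.

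**Formulas.** CKD share of APOL1 positives: c = k·pC / (k·pC + (1 − k)·0.13). Share of the pool enrolled without CKD: (1 − c) / ((1 − c) + c·u).

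**Planning inputs.** c = 0.100 / (0.100 + 0.065) = 0.606. Without CKD: 0.394. Uncoded CKD: 0.606 × 0.4 = 0.242. Share: 0.394 / 0.636 = 62%.

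**Observed prevalence.** Section 9.1 reports 14–15% APOL1 positive. Solving p = k·pC + (1 − k)·0.13 with pC = 20% gives k = 0.01/0.07 = 14% to 0.02/0.07 = 29%. The CKD share c is then 0.200 to 0.386.

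| k | pC | u | Share of pool without CKD | Group (i) per arm (469·c·u) |
|---|---|---|---|---|
| 50% | 20% | 40% | 62% | 114 |
| 50% | 20% | 20% | 77% | 57 |
| 50% | 20% | 60% | 52% | 171 |
| 50% | 26% | 40% | 56% | 125 |
| 14% | 20% | 40% | 91% | 38 |
| 29% | 20% | 40% | 80% | 72 |

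The share falls below half only at corner inputs (for example k = 50%, pC = 26%, u = 60%: 45%). At planning inputs the break-even u is 0.394/0.606 = 65%.

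**Endpoint 3.** Its pool also contains participants whose only CKD codes are stage 1–2, unspecified or diabetic CKD. The stage mix is not given, so no share can be derived.

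**Can the estimate tell the routes apart?** Take planning inputs with 469 per arm: 184.8 without CKD and 113.7 with uncoded CKD. Assume control conversion of 2% and 10% (illustrative; the documents give no rates). Control: (0.02 × 184.8 + 0.10 × 113.7) / 469 = 3.2%.

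- Only new codes in people without CKD rise, 2% to 10%: (18.5 + 11.4) / 469 = 6.4%.
- Only recognition in uncoded CKD rises, 10% to 23%: (3.7 + 26.2) / 469 = 6.4%.

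Both give a difference of 3.2 points, 95% CI 0.4 to 5.9. The estimate is the same for two different effects.

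**Precision in group (i).** At 10% against 23%, the 95% half-width is 1.96 × √((0.09 + 0.1771)/n): 9.5 points at n = 114, 11.9 at 72 and 16.4 at 38.

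**The case against.** The case for leaving the endpoints alone has real weight.

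- The aims and endpoints say documented diagnosis throughout, so the endpoints measure what they name. That stands, and it is why the all-positives comparison should remain.
- A reader might infer that new codes in people enrolled without CKD are mislabelling. The documents do not support that. No CKD at entry means no code and no qualifying laboratory values, which can include people never tested. Section 2.1 says urine tests are missing in up to 30% of participants with CKD, and the intervention prompts them. The Synopsis rationale covers testing as well as diagnosis. Discarding group (ii) codes would remove an intended effect.
- A reader might also infer that a little unsupported coding would produce an apparent benefit. With the rates above, a rise from 2% to 5% in people without CKD gives 4.4% against 3.2%: 1.2 points, 95% CI −1.3 to 3.6. A fivefold rise was needed to exclude zero.
- The grouping is not as clean as coded against laboratory-only. The entry code criterion in Section 5.1 has no look-back, while 5a looks back 24 months, so someone who entered on an older code can still convert.
- Section 9.9 promises estimates and intervals without p values, read conservatively. That limits over-claiming, but the estimate itself remains ambiguous.
- A separate detailed SAP is announced (Section 9.2) and is not among these documents; it may contain such a breakdown. The data could also separate the routes, since Section 9.6 draws eGFR and urine albumin/creatinine from the EHR for the cost-effectiveness model. The limitation lies in the analysis as written.

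**Conclusion.** The point holds as one of interpretation, and is not an error in the endpoints. As planned, a difference on endpoint 3 or 5 cannot be attributed to recognition of existing CKD, new detection, or codes without laboratory support. For endpoint 5, people enrolled without CKD make up about 62% of those who can convert at planning inputs (52–77% for an uncoded share of 60% down to 20%), and about 80–91% at the observed 14–15% APOL1 prevalence. These shares rest on the problem-list gap standing in for missing codes, on APOL1 prevalences taken from other studies, and on reading 5b as N18.x. Read literally, 5b does not count N18.x at follow-up, and people enrolled with neither CKD nor diabetes could convert only through a diabetic-CKD code.

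Two stronger conclusions are tempting. One is that most of those who can convert on endpoint 3 also lack CKD; without the stage mix this cannot be shown. The other is that the main estimate should move to group (i); given the deliberate choice of a documented endpoint and the small numbers there, the documents do not compel it.

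**What to change.** In Sections 9.5 and 10.2:

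1. Keep the all-positives comparison as the stated estimate.
2. Pre-specify that endpoints 3 and 5 are also reported by arm, with difference and 95% CI, within (i) CKD at entry with 3a or 5a = N, and (ii) no CKD at entry. Both are fixed before randomization, so each remains a comparison by randomized arm.
3. Within (ii), show new codes according to whether eGFR or urine albumin/creatinine values in the extracted EHR data support them, without labelling them all as over-coding. State that these values will be extracted for this purpose, since Section 9.6 makes the cost-effectiveness details depend on the main result.
4. Base any claim of improved recognition of existing CKD on group (i).
5. Reconcile E18.x in 5b with N18.x in 5a.

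The cost is a little more analysis. CKD status is already determined for eligibility and 24-month codes are already extracted (Section 7.7). The drawback is wide intervals in group (i) for endpoint 5: about 114 per arm at planning inputs and about 38–72 at the observed prevalence, on the assumptions above.

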### **10.3 Database Management and Quality Control of Data**

The IGNITE PTN CC will develop and manage the GUARDD-US study database and perform internal database quality-control checks. The CC will conduct data audits throughout the course of the trial. These audits are intended to identify data errors, protocol deviations, failure of standardization, missing data, or inconsistencies. Any out-of-range values and missing or inconsistent key variables are flagged and addressed/answered at the site in real time during the data entry process.

All data will be transferred daily from the study database to SAS datasets and stored on the CC's secure servers. The CC will periodically perform additional data quality checks in SAS. Clinical sites may also be given regular feedback directly to discuss issues identified by QC assessments.

### **10.4 Study Close Out**

The end of the trial is defined as the end of participant follow-up in the trial. Upon completion of the study, the IGNITE PTN CC and/or their designee will notify the site of closeout. The CC and/or their designee will ensure that the Investigator's regulatory files are up to date and complete, and that any outstanding issues from previous correspondences have been resolved. Other issues to be reviewed at the closeout include: discussing retention of study files, possibility of site audits, publication policy, and notifying the IRB of study closure.

## **11. ETHICAL AND HUMAN SUBJECTS CONSIDERATIONS**

### **11.1 Institutional Review Board/Ethics Committee Review**

This study will be initiated only after all required documentation has been reviewed and approved by the central IRB according to national and international regulations. The investigator will provide the IGNITE PTN CC or their designee with the study approval documentation before the study may begin. The same is applicable for the implementation of changes introduced by amendments. Where applicable, the investigator must also provide to the IGNITE PTN CC and/or their designee the following documentation:

1. A copy of IRB annual re-approval of the protocol per current Title 21 CFR 312.66 regulations and 1997 International Conference on Harmonization guidelines.
2. IRB approval of revisions to the informed consent documents. Administrative changes (such as a change in address or phone number) must be sent to IRBs/Ethics Committees but do not require their approval.
3. The investigator must submit periodic status reports to their Executive Committee as required, as well as notification of completion of the study and a final report where applicable.
4. The investigator will provide the IGNITE PTN CC or their designee with documentation of all approvals.

### **11.2 Use and Disclosure of Protected Health Information**

For clinical trial sites located in the United States, an Authorization for the use and disclosure of PHI under the HIPAA Privacy Rule [45 CFR § 164.102 *et seq.*] will be obtained from every trial participant prior to, or at the time of, enrollment. The investigator is responsible for obtaining participants' authorizations and signatures, and for explaining the elements of the HIPAA Authorization form. HIPAA Authorization may either be a separate form or included in the study ICF, dependent upon local requirements.

### **11.3 Confidentiality and Privacy**

Participant confidentiality will be maintained throughout the clinical study in a way that ensures the information can always be tracked back to the source data. For this purpose, a unique participant identification code (ID number) will be used that allows identification of all data reported for each participant. Participant information collected in this study and all records will be kept confidential.

Clinical data will be entered into an internet data entry system provided by the CC. The data system includes password protection and internal quality checks, such as automatic range checks to identify data that appear inconsistent, incomplete, or inaccurate. All data collection and storage devices will be password protected with a strong password and all sensitive research information on portable devices will be encrypted. Access to identifiable data will be limited to the study team. If it is necessary to use portable devices for initial collection of identifiers, the data files will be encrypted and the identifiers moved to a secure system as soon as possible. The portable device(s) will be locked in a secure location when it is not in use.

